#### Post-Screening Stage

If eligibility is confirmed, a baseline assessment will take place as quickly as possible (the target will be within 4 weeks). The baseline assessment will take place either in our partner CAMHS services, the local authorities premises, or within the University (UCL) depending on the preference of the foster carer. The research team will liaise with carers about the outcome of the randomisation. Carers will be paid £30 at both the baseline and post-intervention outcome assessment to thank them for their time. Carers will also be reimbursed any travel expenses.

The determination of who must provide consent for a child in foster care to take part in a research study, and how this should be done, is recognised in the literature as a complex problem (Bogolub & Thomas, 2005). An important aim of the current study is to investigate the range of views on how this should be achieved, from local authorities in different regions, and from parents and carers. However, our starting point for the purposes of this study is to follow a procedure used in another NIHR pilot trial being conducted by our group for older children in foster care (6-16 years; NHS REC reference 15/EE/0032). The consent protocol for that study was developed from a review of the literature, and consultation with a local authority Director of Social Care and their legal department. The general principle informing the protocol is that written, informed consent to take part in the study must be received from all parents and from the local authority when holding parental responsibility and that every effort should be made to secure the consent of parents where they do not have sole legal parental responsibility. For children on full care orders, an opt-out letter (with a 14-day period for opting-out) will be used. Children on a full care order may enter the trial without parental consent if the local authority (who may act as Corporate Parent) deems it not in the child's best interests to seek it, or where every attempt has been made to inform parents of the study and to secure consent, but this has failed. For all other children, full written consent will be obtained from the child's parent. Active refusal of consent by a parent would always be respected regardless of the care order. Furthermore, a parent's decision to withdraw their child's involvement once the child has started in the study will again be respected regardless of the care order. Full informed consent would be obtained from all participating foster carers. As the children will all be aged 6 or under they will not provide written consent, but the researchers will be trained to obtain verbal assent in an age appropriate fashion for children old enough to do so (age 4 years and older). For children aged 5-6 years,

information sheets will be provided, with the expectation that the researcher or foster carer will help children read the information. Such forms will be provided prior to the research visits (initially supplied by post to the carer to read to the child, then reiterated by the researcher at the start of the visit), and prior to the first intervention visit for those children assigned to VIPP-FC. The child's social worker will initially make contact with the parent(s), and will provide parents with the information sheets, and obtain verbal consent for their contact details to be passed to the research team. Full written consent will then be sought by a study researcher, which will also provide opportunity for parents to ask more in-depth questions.

Note that for the completion of the screening measures and Disturbances of Attachment Interview (for details, see below; these measures will be conducted in the carers' home) we will only obtain active consent from the foster carer, as it does not directly involve the child, and will initiate the more comprehensive consent process (consent to in-depth assessment and treatment), as described above, after the screening/identification stage. The forms of care order and their respective documentation are listed in Table 1.

#### Additional/Optional consent

The video recordings obtained during the study provide an opportunity to share learning about the processes and outcomes of this study and, particularly, the modified VIPP-FC manual, among practitioners and other relevant professional audiences.

Participants who have consented to taking part in the study and have been randomised to receive CAU+VIPP will be approached to ask if they are willing to give permission for the video recordings to be used for such purposes. We will use Optional Consent to Use Recordings Form to document this, which will be given to participants at the follow-up/post-intervention research visit.

Dissemination of video material will be strictly limited to professional contexts such as intervenor training and professional conferences. We will use software to disguise participants' faces when using recording material in professional conferences. Figures 1 and 2: Consent and study documentation in relation to child's legal status (ICF: Informed Consent Form; PIS: Participant Information Sheet)

*Note*: These same procedures will be used in a limited roll-out for phase 2a (without randomisation).

Figure 3: Process of recruitment, screening, and randomisation for the pilot trial (phase 3)

VIPP- FC Protocol V5 16/01/2019

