# 7.3 DATA MANAGEMENT

The data in this study will be collected and processed in accordance with the Data Protection Act (1998). Management of the data will be overseen by the Chief Investigator [name] with support from the Trial Coordinating Team. The case-series and pilot data will be collected by an experienced research assistant who has been trained to work with high-risk populations. The RA will be blind to treatment allocation, with all data issues related to unblinding being handled by the Trial Coordinating Team. Regular supervision with the Chief Investigator, Trial Coordinating Team and core study team (RAs) will ensure the reliability of data collection. Where necessary the RAs will be fully trained and certified in administering all research measures. For data that requires coding using standardized measures we will employ trained reliable coders, ensuring sufficient Inter-Rater Reliability (IRR) amongst coders.

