# **10.1** HEALTH ECONOMICS

The health economic component of this feasibility study will involve two main elements. The first will involve modification and testing of an appropriate version of the child and adolescent service use schedule (CA-SUS), which has been successfully applied in a pre-school population with autism (Byford et al., 2015) and is currently being implemented in an evaluation of a mental health screening and early intervention

for under 4s, including looked after children (Murphy, 2016). These versions of the CA-SUS will form the basis of a modified version suitable for the current population, with modifications being determined initially by expertise in the research group and subsequently by testing for acceptability and comprehensiveness in the proposed pilot study. Specifically, this initial draft version will then be tested and modified in two main ways. First, we will assess respondents' understanding of the questions and modify the wording or add explanation if anything is unclear. Secondly, we will assess the measure's comprehensiveness in capturing all relevant services. Testing may identify items which are redundant or important services that have been omitted. The CASUS is used as an interview and in the feasibility stage researchers will probe for any missing items and explore (and record) contact with certain key services, such as CAMHS, local authority services and charities about the nature of the contact. The second component will involve exploration of recent literature to assess how realistic it might be to include a measure of health-related quality of life capable of generating quality adjusted life years (QALYs) in this young age group. Without such a measure, it is difficult to make clear resource allocation decisions. However, no measure currently exists for children under 7 years old and although we are aware of research exploring this issue, results are not yet available and are unlikely to be of value for infants and very young children. Review of the most recent evidence may highlight possible solutions, although we do not anticipate there will be a perfect solution for the full age range of 0 to 6. Any subsequent full RCT will therefore be reliant on cost-effectiveness analysis, focusing on the primary clinical measure of outcome.

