# 14.3 SIGNIFICANT EVENTS:

The term *significant event* applies to an event that may occur during participation in the trial that is deemed relevant enough to impact on the study outcomes. As such, a significant event for this study is defined as one of the following:

- A change of placement
- A significant change within placement
- A change of school
- Identification of learning difficulties or diagnosis of a developmental disorder
- A change of social worker
- A change of contact arrangements
- Return to care of birth family
- Other change in care order
- Allegation e.g. maltreatment/abuse
- Other key transition/experience of loss

Significant event reviews will be undertaken by both the RA and therapists throughout the pilot trial. In the case of a significant event occurring, interpretation of the event will be discussed in collaboration with the social worker and carer. The significant events listed above will be recorded in the CRF following consent but will not be reported to the sponsor due to the high frequency at which these events may occur with this sample. However, in the case of death, hospitalisation or maltreatment the sponsor will be informed by the CI, within 5 working days of becoming aware of the event.

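### The data-collecting research assistant is declared blind, but the plan exposes that blinding at several points and does not protect it for the interviewer-rated DAI

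*Protocol*

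**What the plan says.** **Blinding.** Section 7.3 states who gathers the data, "The case-series and pilot data will be collected by an experienced research assistant", and what that person may know: "The RA will be blind to treatment allocation, with all data issues related to unblinding being handled by the Trial Coordinating Team".

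**Recordings form.** Under Additional/Optional consent in section 6.2, the form concerns one arm only: "Participants who have consented to taking part in the study and have been randomised to receive CAU+VIPP will be approached". It is tied to the outcome stage: "We will use Optional Consent to Use Recordings Form to document this, which will be given to participants at the follow-up/post-intervention research visit". The section does not say who hands it over, or whether this comes before or after the assessments.

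**Telling carers the allocation.** Section 6.3 has an unblinded member of the coordination team perform the randomisation and write to carers with the result. It also provides for a telephone call to the foster carer and names no caller. Section 6.2, Post-Screening Stage, says only: "The research team will liaise with carers about the outcome of the randomisation".

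**Significant events.** Section 14.3: "Significant event reviews will be undertaken by both the RA and therapists throughout the pilot trial". It does not say whether the reviews are joint or separate, or whether the RA sees what the therapists report.

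**The outcome.** Section 7.2 labels the DAI the primary outcome. It is a semi-structured interview in which the interviewer probes and then rates each of 12 sections 0, 1 or 2. The five sections on RAD give a total of 0 to 10. Section 10 estimates the post-treatment group difference with a 95% CI (test h.2).

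**The concern.** Foster carers know which arm they are in, and they are the DAI informants. What remains to guard the rating is an interviewer who does not know the arm when choosing probes and assigning scores. The protocol promises such an interviewer but also sets up contacts that could reveal the arm, and it states no safeguard for the DAI against them. It does state one for another measure: section 7.2 has the carer-sensitivity videos scored without knowledge of arm or time point.

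At stake is assessor bias in the DAI difference, which section 10 obtains to constrain effect sizes for later power analyses. The pilot is also meant to show that these instruments can be used within a trial in this setting (section 4.1). It cannot show that assessor blinding works if the plan does not protect it.

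**Working it through.** No figure in the protocol depends on this point, so the check sets the sections side by side.

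**1. Recordings form (6.2 against 7.3).** The form is for the VIPP arm only. If the RA handles it, its presence marks a VIPP family and its absence a usual-care family. The RA collects the pilot data, and no section places a second, unblinded person at the follow-up visit. The text therefore allows the RA to learn the arm there. It does not require it: the handover is described in the passive, with no person and no order relative to the DAI.

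**2. Allocation liaison (6.2 against 6.3).** One section assigns notification to an unblinded coordinator. The other uses a wider term that does not exclude the RA. They can be read together, but nothing makes the reader do so.

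**3. Significant events (14.3 against 7.3).** Only the VIPP arm has study therapists. A therapist's report that reaches the RA identifies the arm, and could do so before the outcome visit. The sentence says that both groups undertake reviews. It does not say that they do so together, and the RA can review events in either arm without learning it.

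**4. Service-use interview (10.1 and 5.2).** In the CA-SUS, "researchers will probe for any missing items and explore (and record) contact with certain key services, such as CAMHS". CAMHS staff deliver VIPP-FC, but section 5.2 also lists treatments that CAMHS teams expect within usual care, and other providers may deliver VIPP-FC. CAMHS contact alone does not reveal the arm. This is the incidental risk of any service-use interview and does not contradict the blinding statement.

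**5. How many families.** The plan randomises 40, 20 per arm. The form could directly identify up to 20 VIPP families. If its absence is informative too, up to 40 ratings are exposed, or 30 at the 75% outcome completion assumed in section 6.1 (0.75 × 40 = 30).

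**6. How much bias.** The protocol gives no DAI standard deviation and no basis for the size of any rater drift, so the bias cannot be derived. For scale only, a drift of 1 point (assumed) divided by the SD (assumed) gives:

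- SD 1.5: 1/1.5 = 0.67
- SD 2: 1/2 = 0.50
- SD 3: 1/3 = 0.33

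The 95% CI half-width for h.2 is t × SD × √(2/n). With SD 2:

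- 20 per arm: 2.02 × 2 × √(2/20) = 1.28 points
- 15 per arm: 2.05 × 2 × √(2/15) = 1.50 points

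A 1-point drift would lie within that sampling uncertainty. This converts units and is not evidence that such a drift would occur.

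**The case against.** The strongest case against runs as follows.

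- **Silence is not contradiction.** A form handed over after the DAI cannot change a rating already made. Section 6.3 already provides an unblinded coordinator, and section 7.3 sends unblinding issues to that team. The protocol does not say that the follow-up DAI and the form share one session; at entry the DAI took place in the carer's home, apart from the baseline visit. This stands. A reader might infer that the primary outcome would be collected unblinded, or that whoever runs the visit must know the arm. The documents do not support either reading.
- **The events sentence does not describe joint work.** This also stands. None of the listed events identifies the arm by itself. What remains is that no separation between therapists' reports and the RA is stated.
- **The term research team is generic and section 6.3 is the specific rule.** This is a reasonable reading, but a plan that depends on one blind person should not rely on it.
- **The consequence is limited.** The numeric progression thresholds in section 13.1 concern treatment retention, outcome completion and RAD identification; none uses the DAI difference. Test h.2 is descriptive and carries its own caution, the most appropriate primary outcome is still to be identified, and the carer is unblinded whatever the interviewer knows. All of this stands and lowers the weight of the point. It does not remove it, since h.2 is meant to inform later power analyses.

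**Conclusion.** The concern holds in a limited form. The protocol declares the RA blind, then describes a one-arm form at the follow-up visit, unrestricted liaison about allocation, and event reviews by both RA and therapists, with no protection stated for the DAI rating. This exposes the blinding; it does not show that it would be lost.

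The exposure is at most 20 VIPP families directly, or 40 ratings if absence of the form is also read. The size of any bias is unknown. The result at risk is test h.2. Consent, randomisation and attendance proportions and the thresholds in section 13.1 are little affected, and full blinding of the DAI is out of reach because of the carer.

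The conclusion assumes that the RA conducts the follow-up DAI, as section 7.3 implies by giving pilot data collection to that role. It is worth correcting because the remedy is specific and nearly free, but it does not invalidate the pilot.

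**What to change.** 1. **Section 6.2, Additional/Optional consent:** state that the unblinded coordination team sends or gives the recordings form, and only after all outcome ratings for that family are complete.
2. **Section 6.2, Post-Screening Stage:** replace the research team with the unblinded member of the trial coordination team, to match section 6.3.
3. **Section 14.3:** route therapists' event reports to the unblinded coordinator and keep them from the RA.

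Two low-cost additions are optional and do not correct an error: rate the DAI before the CA-SUS interview, and record the assessor's guess of arm once the DAI is scored.

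The cost is a few lines of protocol text and a little more work for an unblinded role that already exists. This version is dated 16 January 2019 and its timetable runs outcome assessment to June 2019, so on that timetable the remaining follow-ups could still be protected.

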#### 6.3 RANDOMISATION (PHASE 3)

Participants will be individually randomised in a 1:1 ratio to one of the two treatment arms, CAU + VIPP-FC or CAU-only. Randomisation with minimization will be employed, with minimization factors age (<=4 versus >4), gender and site. Minimization will include a random factor, as implemented in the minimisation program Simin (Wade, Pan, Eaton, Pierro & Ong, 2006). Randomisation will be requested by a member of the research team following completion of all necessary screening and consent procedures, and will be performed by an unblinded member of the trial coordination team. The allocation list will be held in the Trial Master File. We will write to the child's social worker, and VIPP intervener – the latter for those allocated to VIPP-FC. The foster carer, and the individual(s) giving consent on behalf of the child (the parent and/or local authority social worker with parental responsibility as appropriate, see consent section) will be notified of the outcome by letter by the unblinded member of the trial coordination team. The foster carer will also be contacted by telephone (target within 24 hours) to ensure a timely initiation of intervention.

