behavioural signs of RAD that could indicate a potential RAD diagnosis. In-depth assessments of RAD will determine whether sufficient RAD symptoms are present for the child to enter the pilot trial. For the screening phase, active consent will be provided by the foster carer only, as it does not involve direct contact with the foster child. A letter will be sent to all parents explaining the study and offering them the opportunity to ask questions and opt-out if they have concerns. Parents will be given a minimum of two weeks to notify the Local Authority or the research team if they wish to opt out from the screening. If a child meets the RAD threshold full consent from those holding parental responsibility would then be obtained and the child and foster carer (if all parties are happy to proceed) will enter the pilot trial. Prior to randomisation, the child and foster carer will be invited to attend a baseline assessment and then randomised individually to VIPP-FC or CAU in a 1:1 ratio, stratified by age, gender and site. As this is a pilot trial 40 cases would be randomised in total, which is sufficient to test the feasibility questions described below and estimate approximate confidence intervals for key study parameters. VIPP-FC will be delivered in-home by trained CAMHS practitioners or other appropriately qualified VIPP-trained interveners. Baseline and end of treatment measures will include validated diagnostic assessments of RAD and co-occurring conditions, security of attachment (including disorganized attachment), sensitivity of parenting, child adjustment, carer wellbeing, and the CA-SUS measure of service use. In addition to these outcome measurements, we would also conduct qualitative interviews regarding carers' experiences of the programme and perceptions of VIPP among social workers and VIPP interveners. As a pragmatic study, we would aim to include as representative a group of children as possible and therefore we would aim to apply minimal exclusions based on comorbidity or type of foster care. The pilot RCT will allow us to:

- A. Test the feasibility of identifying sufficient numbers of appropriate cases through social care using appropriate screening instruments and diagnostic assessments of cases screening positively for RAD across several local authorities and locales (rural and urban).
- B. Test the feasibility of recruiting and consenting foster families with children with RAD to an RCT (numbers contacted, consented).

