#### Child:

- (a) living with foster carer(s) in a placement planned to be at least 4 months;
- (b) lived with foster carer for at least 4 weeks
- (c) presence of DSM-5 defined RAD\*
- (d) aged between 11 months and 6 years

Note: as outlined below, because of the uncertain prevalence of RAD in UK foster care populations, the RAD eligibility criterion will be reviewed after 15 cases have been assessed. If fewer than 3 (out of 15) cases scoring over the screening threshold (> 66th percentile on screening measure) actually meet diagnostic criteria, we propose to include sub-diagnostic cases with elevated symptoms in the feasibility trial based on the screening threshold (defined below).

For the pilot case series, we will include a mix of cases that meet the RAD diagnosis and those falling short of the diagnostic threshold in order to explore the suitability of the intervention for both groups of children and expedite the rapid progress of manual refinement.

\*If during the RCT phase number of participants deemed eligible is inadequate to allow delivery of the final study aim (i.e. run the modified VIPP programme for foster care) we will expand the eligibility criteria to include carers with children who do not necessarily meet the RAD criterion.

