#### Pilot RCT

For Phase 3 (the pilot RCT) we will again undertake a screening process to identify children in foster care with RAD. We will then randomise 40 children (and their carers) to receive either VIPP (plus care as usual) or care as usual only. Based on data obtained from the Department of Education from 2014 (which we have corroborated against a selection of figures obtained in 2016 from our participating local authorities) we expect the full population of children in foster care in our target age groups across sites to be in the region of 700. Previous research experience with this population and on the basis of our small pilot screening, we would expect more than 80% of foster carers to take part in the initial screening and return the questionnaires. This estimate seems reasonable, since in the study of Green et al. (2014) of 523 foster families who were approached, only 56 refused (a further 57 were ineligible). Conservatively therefore we will aim for a sample size for the screening stage of 500. In order to identify cases likely to be diagnosed as RAD we will choose cases above the highest 66th percentile for symptoms of RAD (initially based on normative data), leading to a sample size of 150 who would be invited to take part in a more in-depth assessment. We expect a minimum of two thirds of those to agree to take part and complete the assessment. In the randomised controlled trial of the Fostering Changes programme, (Briskman et al., 2012) 77/125 took part in the intervention (following a higher rate of initial interest and questionnaire return), so two-thirds agreeing to an initial assessment is a conservative estimate. From this pool of 100 children we would therefore have scope to identify at least 40 cases that would be eligible for treatment as long as the prevalence of RAD in the high-scoring screened group was 50% (allowing for a further 10% dropout at this stage). Note that we would seek to obtain consent to treatment at the in-depth intake assessment stage, which is why we estimate the throughput of cases to be lowest at this point. As noted already, we lack reliable information concerning the prevalence of RAD in UK foster care and so the 50% prevalence within the population of children exceeding the symptom threshold is subject to uncertainty. Consequently, we propose an interim analysis after 15 cases have been assessed to establish whether the proportion of RAD cases is below this expected proportion. The lower bound of the 95% confidence interval around a proportion of .50 is .22 with a sample size of 15. Thus, identification of fewer than 3 cases out of 15 would suggest that the prevalence is lower than .50. In this event, we propose to widen the eligibility criteria to include children scoring over the screening threshold, but not meeting full RAD diagnostic criteria.

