#### Screening and identification stage

As noted above, the screening process we envisage will be essential to the success of this project and will depend on an effective collaboration with local authorities, who will send out information sheets, initial consent forms and screening measures to all foster carers in the study localities. In addition, local

authorities will send out a letter to all parents explaining the study and the opting-out process, including contact details of the research team. In Phase 2A we will work with up to two local authorities, and will screen approximately 100 children. In phase 3 we will aim for a minimum screening sample of 500 foster carers from 6-10 local authorities. In both cases, all foster carers or special guardians registered with the local authority caring for children under 7 will be sent an information sheet, screening measures, a consent form and contact details of the research team so that they may ask questions if they wish. Screening measures and completed consent forms will be returned using a pre-paid envelope by foster carers to the University or completed online via study database, Redcap. Letters will also be sent to foster care agencies with information and contact details of the research team that may be given to potential participants registered with these organisations. Where self-referrals are received, foster carers will be asked for the child's social worker's details in order for the local authority to initiate the screening process, including contacting the birth parents. As with the families that are contacted through the local authorities, self-referrals will have the contact details of the research team if they wish to discuss the study in more detail. A minimum two-week period will be given between sending out the letter to parents and initiating the child's participation in the study.

Once initial consent forms (paper and online) and screening measures have been received by the research team, they will contact participants, thanking them for their response and re-iterating the research process. Invitations and follow-up phone calls will be made to all foster carers reporting RAD symptoms over the screening cut-off to take part in a face-to-face interview assessment to confirm eligibility (establishing diagnostic status). This interview would take place at the foster carer's home.

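### If eligibility is widened, diagnosed and sub-diagnostic children are allocated without balancing on RAD diagnosis; adding it as a minimisation factor would be a cheap, minor improvement

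*Protocol*

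**What the plan says.** Section 6.3 states that "Participants will be individually randomised in a 1:1 ratio", by minimisation with a random element, "with minimization factors age (<=4 versus >4), gender and site". Section 4.2 (Phase 3) names the same three factors, "stratified by age, gender and site", and gives the size: "As this is a pilot trial 40 cases would be randomised in total".

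Two clauses allow the population to become mixed:

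- **Interim rule.** Section 4.4 sets the condition, "If fewer than 3 (out of 15) cases scoring over the screening threshold" meeting diagnostic criteria. Section 6.1 states the consequence: "we propose to widen the eligibility criteria to include children scoring over the screening threshold, but not meeting full RAD diagnostic criteria".
- **Starred note in Section 4.4.** If too few children are eligible during the RCT, "we will expand the eligibility criteria to include carers with children who do not necessarily meet the RAD criterion".

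Diagnosis is known before allocation. Section 6.2 describes a "face-to-face interview assessment to confirm eligibility (establishing diagnostic status"), and Section 6.3 places randomisation after screening and consent. Section 7.2 relies on the DAI for the RAD diagnosis and also names the DAI as the primary outcome. Nothing in the protocol adds diagnosis, or the baseline DAI score, to the allocation once eligibility is widened.

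**The concern.** The three-factor rule suits a trial in which every child has the diagnosis. The protocol also plans for a trial in which most children may not, and it keeps the same rule. The omitted variable defines the target population, comes from the instrument that measures the primary outcome, and is already on file when randomisation is requested.

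If widening happens and few diagnosed children enter, they may by chance fall mostly in one arm. Two things could suffer:

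- Session attendance, treatment completion and satisfaction (Section 10, item D) and the in-depth interviews (Section 7.2) concern families who receive VIPP-FC. If only one or two of them have a child with diagnosed RAD, the pilot shows little about delivery to that group.
- The post-treatment group difference (test h.2 in Section 10) is meant to constrain effect sizes for later power calculations. It would carry any difference in case mix between the arms.

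**Working it through.** **The plan's own trigger.** Section 6.1 gives .22 as the lower 95% bound for a proportion of .50 with n = 15. This is reproduced by .50 − t(.975, 14) × √(.25/15) = .223. The rule fires at 2 or fewer diagnoses among 15.

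**Number of RAD children among 40 (K).** At the trigger, 40 × 2/15 = 5.3, so about 5. The exact 95% interval for 2/15 is 1.7% to 40.5%, or about 1 to 16 children of 40. This assumes that the randomised children have the same mix as those assessed. The protocol gives no figure for K.

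**Chance split, ignoring the other factors.** With 20 per arm, the number of RAD children in VIPP-FC is hypergeometric:

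P(X = x) = C(20, x) × C(20, K − x) / C(40, K)

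- K = 5: P(X = 0) = 15,504/658,008 = 0.024 and P(X = 1) = 96,900/658,008 = 0.147. One or none in VIPP-FC: 0.171. A 4:1 or worse split in either direction: 2 × 0.171 = 0.342.
- K = 8: P(X ≤ 2) = 0.118. A 6:2 or worse split: 0.235.

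| K | Split | Probability |
|---|---|---|
| 4 | 3:1 or worse | 0.61 |
| 5 | 4:1 or worse | 0.34 |
| 6 | 5:1 or worse | 0.18 |
| 8 | 6:2 or worse | 0.24 |
| 10 | 8:2 or worse | 0.07 |
| 16 | 12:4 or worse | 0.02 |

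**Do the three stated factors help?** Minimisation was simulated under these assumptions: 5 sites, probability 0.8 for the favoured arm, factors unrelated to RAD status, 3,000 runs. The table gives the chance that at least 75% of RAD children fall in one arm.

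| K | Age, gender, site | Plus RAD diagnosis |
|---|---|---|
| 4 | 0.62 | 0.45 |
| 6 | 0.19 | 0.04 |
| 8 | 0.23 | 0.04 |
| 10 | 0.08 | 0.002 |

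The first column matches the simple hypergeometric values, so the stated factors give no protection when unrelated to RAD. With K = 4, the fourth factor also reduces the chance of all four falling in one arm from 0.11 to 0.03.

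**Effect on h.2.** The shift in an unadjusted difference is the difference in RAD share between arms times the DAI gap between diagnosed and sub-diagnostic children. With an assumed gap of 1 SD:

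- A 20-point imbalance gives 0.20 × 1 = 0.2 SD. At K = 8 this is a 6:2 split (6/20 − 2/20), so an imbalance that large or larger has probability 0.24.
- At K = 5, a 4:1 split is 15 points (4/20 − 1/20), or 0.15 SD. Reaching 20 points needs 5:0, with probability 0.047.

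The standard error of a two-arm mean difference is √(2/20) = 0.32 SD with all 40 children, and √(2/15) = 0.37 SD with the 30 completers assumed in Section 6.1.

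**The case against.** The strongest reply is that nothing here is an error. Sections 4.2 and 6.3 agree on the factors, choosing them is a matter of design, and the issue arises only if eligibility is widened. The risk is chance imbalance, which the confidence interval for h.2 already reflects. Baseline adjustment, which an analysis plan may specify, could remove much of any shift. The 1 SD gap is an assumption, and it may be smaller because the added children also have raised symptoms. All of this stands.

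A reader might infer more than the documents support, in three ways:

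- **That the pilot's conclusions depend on this balance.** They do not. Section 6.1 justifies 40 by the precision of proportions. The numerical stop criteria in Section 13.1 (treatment retention, outcome completion and RAD identification) compare no arms. Section 10 lists no analysis by RAD status within arm.
- **That large shifts in h.2 are likely.** With 20 RAD children among 40, the RAD share would differ by 20 points or more with probability 0.34. That scenario fits the interim rule poorly: at 50% prevalence, fewer than 3 of 15 has probability 0.0037. It is plausible only through the vaguer starred note.
- **That balancing would let the pilot speak for RAD.** With 4 to 8 RAD children, perfect balance still leaves only 2 to 4 in VIPP-FC. The main limit is how few there are.

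One part of the reply does not hold. An analysis plan can adjust an estimate, but it cannot put diagnosed children into an arm that received almost none.

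**Conclusion.** The point holds as a conditional, minor improvement. If eligibility is widened, allocation ignores a variable that is known before randomisation, defines the target population and comes from the primary outcome instrument. With about 5 RAD children, the number implied by the trigger, a 4:1 or worse split is about a one-in-three event, and one or none in VIPP-FC about one in six. Any shift in h.2 is modest: 0.2 SD under the stated assumptions, which is below its standard error. The result rests on the assumed number of RAD children and on age, gender and site being unrelated to RAD status. With about 16 RAD children, marked imbalance is unlikely. The documents do not support calling this a bias or a threat to the progression decision.

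**What to change.** In Section 6.3, and in the matching sentence of Section 4.2, add DAI diagnosis of RAD (met or not met) as a fourth minimisation factor from the first child, using the determination already made for eligibility. While only diagnosed children enter, the factor has one level and does nothing. Once sub-diagnostic children are admitted it takes effect, and the diagnosed children already randomised count in its totals.

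The cost is one phrase in each section, one setting in the minimisation program, and slightly weaker balance on age, gender and site after widening. No extra data are needed and the sample stays at 40. The gain is clear with 6 to 10 RAD children and limited with about 4. The change does not increase their total number, so the report should give the count of diagnosed children in each arm if widening occurs.
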